12.4.12. Interim Futility Analysis

The study will include an interim futility analysis as defined in the SAP. For the futility analysis, the conditional power of showing statistically significant evidence of benefit on the primary endpoint will be calculated for each dose group. If the conditional power is less than 20% in either dose, continuing to enter infants in that dose group will be considered statistically futile.

An independent statistician will perform the futility analysis. This statistician will not be involved in the preparation of the statistical analysis plan or in other aspects of the trial. The statistical analysis performed during the futility interim look will be presented as defined in the SAP to an independent Data Monitoring Committee (DMC), which will review the results and make a recommendation regarding continuing the study, stopping the study, or discontinuing recruitment into one dose group. The DMC will base its recommendation on trial continuation on the totality of evidence available to it, rather than only on the statistical futility criterion. Because the only reason to recommend stopping the study, or stopping one dose, is futility (or safety) and not efficacy, this analysis does not compromise the Type I error rate.

The Sponsor will be blinded to all efficacy and safety data. Only the final DMC recommendation will be provided to the Sponsor.

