1.3.3 Sample Size and Statistical Power Considerations

Presentation of sample size is based on the hypothesis that NFE in either treatment group is shorter than in the placebo group. Based on limited historical data (Phase 2), the

Confidential Page 14 of 40

conservative mean is 8.0 days for the placebo group and 6.6 days for each of the 2 active dose groups. This assumes a standard deviation of 3.5 days for each group.

The analysis will be based on a nonparametric test. The NFEs for each infant in the FAS will be ranked from shortest time (the best outcome) to longest time. Infants who do not achieve full enteral feeding and also experience necrotizing enterocolitis (NEC) will be assigned the next set of ranks; all the infants experiencing NEC will be ranked in terms of their time to NEC (the earlier the worse) and will be assigned ranks one greater than the rank of the longest time to achieve NFEs. All infants who do not achieve full enteral feeding and die will be assigned the next set of ranks, again with the earliest deaths assigned the largest (i.e. worst) rank. Thus, each infant who has achieved EN or who has died or suffered NEC will have a recorded rank.

Randomization will be stratified by center and by gestational age group. The statistical analysis will stratify the infants by gestational age group and region (North America, Europe, and Israel), but not by center. Because the analysis will be based on ranks, a van Elteren test will be used to compare NTRA-2112 to placebo. To calculate sample size, an independent groups t-test for 85% power to account for the reduced power of the non-parametric test was used (i.e., expect that a t-test with 85% power to have at least 80% power when the van Elteren test is applied). A two-side 5% test will be used to compare each active dose to placebo. These calculations give N = 115 infants per group. To account for the reduction in power caused by potential missing data, the sample size was increased to 130 per group or a total sample size of 390

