1.7 MULTIPLE COMPARISONS/MULTIPLICITY

This trial has one primary and one key secondary endpoint. The study is comparing each of two doses to placebo; a hierarchically ordered testing procedure will be used to test the primary endpoint, then secondary endpoint for the high dose first, then for the lower dose. Nutrinia believe that insulin as a growth factor will have effect with both doses. We expect that there is an opportunity for exploring higher dose that may yield a more favorable clinical effect than the lower dose that was used in the phase 2. Thus for that reason, a hierarchal approach is now being considered in the analysis. This procedure will preserve the type 1 error rate of 5% overall. The detailed testing procedure and the stopping rules are described below.

- 1. The NTRA $-2112\ 2000\ \mu\text{IU}$ Insulin/ml group is compared with the placebo group for the primary endpoint using a two-sided test at the 0.05 significance level.
 - If the null hypothesis is not rejected, no further comparisons are made.
 - If the null hypothesis is rejected, comparisons continue in the next step.
- 2. The NTRA $-2112\ 2000\ \mu\text{IU}$ Insulin/ml group is compared with the placebo group for the key secondary endpoint using a two-sided test at the 0.05 significance level.
 - If the null hypothesis is not rejected, no further comparisons are made.
 - If the null hypothesis is rejected, comparisons continue in the next step.
- 3. The NTRA $-2112\ 400\ \mu\text{IU}$ Insulin/ml group is compared with the placebo group for the primary endpoint using a two-sided test at the 0.05 significance level.
 - If the null hypothesis is not rejected, the final comparison will not be made.
 - If the null hypothesis is rejected, the final comparison in the next step will be made.
- 4. The NTRA $-2112\ 400\ \mu\text{IU}$ Insulin/ml group is compared with the placebo group for the key secondary endpoint using a two-sided test at the 0.05 significance level.

Confidential Page 18 of 40

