For the futility analysis, the conditional power of showing statistically significant ($P \le 0.05$) evidence of benefit on the primary endpoint at the final analysis will be calculated for each dose group. Conditional power will be calculated from the z-value based on the interim analysis, treating the primary endpoint as a continuous variable, approximately following the normal distribution. The conditional power will be calculated based on the observed interim trend of effect size, not the original expectation in the sample size calculation. If the conditional power is less than 35% in either dose, continuing to enter infants in that dose group will be considered statistically futile.

The futility analysis results, including the calculated conditional power for each dose group and summaries of selected key safety parameters (adverse events, lab tests, physical exams, and vital signs), will be presented to the Data Monitoring Committee, who will review the results and make a final recommendation regarding the continuation or discontinuation of one or both dose arms. The recommendation will be based on the conditional power and the totality of the clinical data available.

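### The SAP lets the high dose alone be dropped for futility, yet both confirmatory low-dose tests depend on high-dose success, so a low dose that continues has little chance of being claimed

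*SAP*

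**What the plan says.** SAP 3.1 computes conditional power for each dose from the observed interim trend. The target is P≤0.05 on that dose's own primary comparison at the final analysis. The rule is symmetric: "If the conditional power is less than 35% in either dose, continuing to enter infants in that dose group will be considered statistically futile". The DMC is then to "make a final recommendation regarding the continuation or discontinuation of one or both dose arms". Protocol 12.4.12 lists the same options: "continuing the study, stopping the study, or discontinuing recruitment into one dose group".

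SAP 1.7 sets a fixed sequence, each step at two-sided 0.05: high-dose primary, high-dose key secondary, low-dose primary, low-dose key secondary. After each of the two high-dose steps it says: "If the null hypothesis is not rejected, no further comparisons are made". SAP 2.2.1.1 and 2.2.1.2 tie the primary and key secondary analyses to that sequence.

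Protocol 12.1.1 and 12.4.5 had used a Bonferroni split, under which either dose could succeed alone. SAP section 4 replaces it with the hierarchy, and protocol 12.4 gives the SAP precedence.

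**The concern.** With a Bonferroni split, a dose-by-dose futility rule is coherent, because losing one dose leaves the other's test intact. With a high-dose-first sequence it is not symmetric. Dropping the low dose costs the high dose nothing, but dropping the high dose removes most of the low dose's route to a claim. No section of either document covers that case: there is no skipping of steps, no re-ordering and no transfer of alpha.

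The conditional power shown to the DMC adds to the problem. The low-dose figure is the chance of P≤0.05 on the low-dose comparison alone and ignores the two high-dose results that must come first. A DMC following the SAP could see a promising low dose, drop only the high dose, and keep randomising preterm infants to an arm with little chance of a confirmatory result. Protocol 5.2 names the low dose as the level with earlier clinical data. A repair made after unblinded interim results would be hard to defend.

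**Working it through.** **Inputs.** SAP 1.3.3 takes a common SD of 3.5 days. Its other planning values are: "conservative mean is 8.0 days for the placebo group and 6.6 days for each of the 2 active dose groups"; for the test level, "A two-side 5% test will be used to compare each active dose to placebo"; and, for power, "an independent groups t-test for 85% power to account for the reduced power of the non-parametric test was used". The result is 115 per group, raised to 130 for missing data. SAP 3.1: interim once at least 150 are randomized, so about 50 per arm at 1:1:1; cut at 35%.

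**The plan's own figure.** The effect is 8.0 − 6.6 = 1.4 days, or 1.4/3.5 = 0.4 SD. The normal formula gives n = 2 × (1.960 + 1.036)² × (3.5/1.4)² = 112.2, so 113. The exact t calculation gives 114, and power at 115 is 85.6%. The SAP's 115 is reproduced closely.

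**What the 35% cut means.** Under the observed trend, CP = Φ((z/√t − 1.96)/√(1 − t)). With t = 50/115 = 0.435, CP = 0.35 at z = √0.435 × (1.960 − 0.385 × √0.565) = 1.10. That is 1.10 × 3.5 × √(2/50) = 0.77 days. With 130 at final, the cut is z = 1.03, or 0.72 days. A dose with the full design effect has expected interim z = 1.4/0.70 = 2.0, so it is flagged with probability Φ(1.10 − 2.00) = 18%.

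**High dose flagged, low dose not.** Simulation of 1,000,000 trials per scenario, normal outcomes, shared placebo, 50 per arm at interim, 115 at final, low-dose effect 1.4 days throughout:

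| True high-dose effect | High dose alone flagged | Low dose then reaches nominal P<0.05 | Step 1 passes, arm held at 50 | Step 1 passes, arm continued to 115 |
|---|---|---|---|---|
| 1.4 days | 10.7% | 88% | 7% | 59% |
| 0.7 days | 39% | 90% | 1.6% | 15% |
| 0 | 68% | 92% | 0.2% | 1% |

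The last three columns are conditional on the high dose alone being flagged. Step 1 is the high-dose primary test against the full placebo arm; the high-dose key secondary must also be rejected before any low-dose test. With 130 per arm at final, the first row becomes 9.9%, 91% and 8% for the first three figures.

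**If the dropped arm is larger than 50.** Enrolment may continue during follow-up and data lock. The documents give no accrual rate, so 65 and 80 are assumptions. With both effects at 1.4 days, step 1 passes 23% of the time at 65 and 37% at 80. With no high-dose effect it stays under 1%.

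**Fallback split.** At 115 per arm the expected final z is 0.4 × √(115/2) = 3.033. Power is Φ(3.033 − 1.960) = 85.8% at 0.05, Φ(3.033 − 2.005) = 84.8% at 0.045, and Φ(3.033 − 2.807) = 59% at 0.005. Within the branch where only the high dose is flagged, low-dose power at 0.005 is 57%, 62% and 66% in the three scenarios.

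**Unadjusted promotion.** Suppose the low dose is moved to step 1 at the full 0.05 whenever the high dose is dropped. With neither dose effective and 115 per arm, the chance of a false benefit claim is 2.8% if the futility rule also binds the low dose and 3.4% if it does not, against a one-sided target of 2.5%.

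**The case against.** The sponsor chose a high-dose-first hierarchy openly and gives its reasons in SAP 1.7 and section 4. As written, the overall error rate is protected. Estimates with 95% confidence intervals are already planned for each dose (SAP 2.2.1.1). The 35% rule is guidance, since the DMC also weighs the rest of the clinical evidence and may stop or continue both arms. The DMC charter, which SAP 3.2 says holds the futility guidelines, is not among the documents. All of this stands, and it makes the point one of clarification rather than of invalid inference.

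Three stronger readings are tempting and not supported.

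- A reader might infer that the low dose can then never be claimed. Stopping entry does not remove randomized infants from the full analysis set (SAP 1.5.1), so step 1 can still be run. If both doses work and the arm has grown past 50, its chance of passing is not negligible.
- A reader might charge the 39% and 68% flag rates to the futility rule. In those branches step 1 would have passed only about 15% or 1% of the time had the arm continued, so the block comes mainly from the hierarchy.
- A reader might infer that the dose-by-dose rule is a leftover from the Bonferroni scheme. The revision history shows that section 3.1 was revised in V1.3, after V1.2 had changed the testing procedure. The documents do not show whether the mismatch was noticed.

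The objection does not supply the missing rule. Dropping one arm is an explicit option, and the SAP, which governs the final tests, does not say what follows from it.

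**Conclusion.** The concern holds in a limited form and should be fixed before the interim. SAP 1.7 and 3.1 do not fit together when only the high dose is dropped. The low dose is then unlikely to be claimable, however good its data.

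The scenario that measures harm from the dropping decision itself is the one in which both doses work. The high dose alone is flagged in about 11% of such trials. In those, step 1 would have passed 59% of the time had the arm continued, against 7% at 50 infants or 23% to 37% at an assumed 65 to 80, before the high-dose key secondary is considered. The 11% is an advisory flag rate and should not be read as the chance that the arm is dropped.

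The figures assume about 50 evaluable infants per arm at interim, 115 at final and normally distributed outcomes; they ignore the ranking of NEC and death. Only the two confirmatory low-dose tests are affected, because the other secondary tests are exploratory.

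**What to change.** Reconcile SAP 1.7 and 3.1 before the interim, in one of two ways.

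- **(a) Keep the hierarchy and state its consequence.** Say in both sections that dropping the 2000 µIU/ml arm counts as non-rejection at step 1, and that low-dose results are then estimates with confidence intervals only. Present the low-dose conditional power to the DMC with that consequence attached. This costs wording only. It also settles whether step 1 is run on a truncated arm.
- **(b) Keep the low dose claimable.** Pre-specify an error-controlling fallback, for example 0.045 for the high dose and 0.005 reserved for the low-dose primary test, and write out the full order including the key secondary tests. The two levels sum to 0.05, so the overall rate is kept. High-dose power falls from about 85.8% to 84.8%, and the low dose has about 57% to 66% power if only the high dose is dropped.

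Do not move the low dose up to the full 0.05 without adjustment. If the futility rule does not bind the low dose, the false-benefit rate rises to about 3.4% against 2.5%.

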3.2 DATA MONITORING COMMITTEE

An independent DMC is established and responsible for monitoring the trial to ensure the safety of patients in the trial. The DMC will review safety data and will make recommendations whether to continue or terminate the study. The DMC analyses and operations will be formally separated from the sponsor, the investigators, and the Steering Committee.

The DMC's responsibilities are to:

- Review safety and efficacy data during the study with consideration for the impact on patient safety, as well as the ethics of continued study conduct.
- Conduct review results of interim and final safety evaluations of the study, including an interim analysis for futility.
- Consider factors external to the study when relevant information becomes available, such as scientific or therapeutic developments that may have an impact on safety, scientific integrity, or the ethics of conducting the study.
- Review and evaluate ad hoc safety issues concerning the study that arise from any Serious Adverse Drug Reaction (an adverse event that might be related to the study drug, i.e. a causal relationship between exposure to the study drug and the serious adverse event is at least possible) or other safety matters at the request of the sponsor.
- Make recommendations to the sponsor concerning continuation/termination, or other modifications of the study based on the observed beneficial or adverse effects of the study drug.
- Operate according to the procedures described in the DMC charter.

A DMC Charter has been developed that defines the DMC organization, responsibilities, relationship with other trial entities, and the purpose and schedule of the DMC meetings.

Confidential Page 36 of 40

Statistical Analysis Plan V1.3 SAP Date: 06APR2018

The charter provides the procedures for ensuring confidentiality, proper communication, scopes of the interim data to be presented, and the statistical guidelines for interim futility analysis by the DMC.

4 SUMMARY OF MAJOR CHANGES IN THE PLANNED ANALYSES

The PP set is defined differently from the protocol, but the difference is not considered to be major. The approach described in the protocol of using methods that separate the reasons for noncompliance from the effect of study drug (e.g. Robins, 1989) will not be followed. Instead, the more common approach of defining a PP set based on study compliance will be adopted. PP analysis will only be supportive of the primary intention-to-treat analysis based on the FAS.

The treatment difference between two NTRA-2112 doses will be estimated for the primary endpoint, key secondary endpoint, exploratory secondary endpoint, and other endpoints.

The Bonferroni correction was described in the protocol for testing the primary and the key secondary endpoints simultaneously for each dose level. Nutrinia believe that insulin as a growth factor will have effect with both doses. We expect that there is an opportunity for exploring higher dose that may yield a more favorable clinical effect than the lower dose that was used in the phase 2. Thus for that reason, a hierarchical approach is now being implemented in the analysis. This procedure is described in Section 1.7 of this SAP to allow testing the primary endpoint, then secondary endpoint for the high dose first, then for the low dose while maintaining the type 1 error rate of 5% overall.

The sample size was re-calculated in Section 1.3.3 due to the change in the testing procedure stated above.

Section 2.2.1.3.2 was modified to allow longer time, up to 180 days, to observe the actual time for discharge or being ready to be discharged (NRD).

Section 2.2.1.7 was added for a sensitivity analysis using the baseline enteral feeding volume to break the tied NFE ranking.

Section 2.2.1.8 was added for a summary of number and percent of infants who achieve the complete and partial enteral feeding success for each treatment.

The reporting periods for AE reporting have been further defined in Section 2.3.2.1.

Section 3.1. The timing of the sample size re-estimation relevant to the futility analysis is further clarified. The conditional power is raised from 20% to 35%. Based on the conditional power and the totality of the clinical data available at the futility analysis, the DMC will recommend to continue or discontinue one or both dose arms. The sponsor will consider increasing the total sample size up to 450 patients based on the sample size

Confidential Page 37 of 40

re-estimation.

6 APPENDIX

6.1 Partial dates for adverse events and prior/concomitant medication

Dates missing the day or both the day and month of the year will adhere to the following conventions to classify treatment-emergent AEs and to classify prior/concomitant medications. When the conventions are applied to infants, if an imputed date is before infant's birthday, the date should be set on the birthday. For example, if a missing date of AE is set on January 1, but January 1 is before infant's birth, then the date of AE should be set on the birthday.

Adverse events

The missing day of *onset* of an AE will be set to:

First day of the month that the event occurred, if the onset YYYY-MM is after the YYYY-MM of first study treatment

The day of the first study treatment, if the onset YYYY-MM is the same as YYYY-MM of the first study treatment

The date of informed consent, if the onset YYYY-MM is before the YYYY-MM of the first treatment.

The missing day of *resolution* of an AE will be set to:

The last day of the month of the occurrence. If the subject died in the same month, then set the imputed date as the death date.

If the *onset* date of an AE is *missing* both the *day and month*, the onset date will be set to:

January 1 of the year of onset, if the onset year is after the year of the first study treatment

The date of the first treatment, if the onset year is the same as the year of the first study treatment

The date of informed consent, if the onset year is before the year of the first treatment

If the resolution date of an AE is missing both the day and month, the date will be set to:

December 31 of the year of occurrence. If the subject died in the same year, then set the imputed date as the death date.

Confidential Page 39 of 40

Statistical Analysis Plan V1.3 SAP Date: 06APR2018

Prior/concomitant medication

The missing day of *start date of a therapy* will be set to the first day of the month or the infant's birthday, whichever is later, that the event occurred.

The missing day of *end date of a therapy* will be set to the last day of the month of the occurrence.

If the *start date of a therapy* is missing both the *day and month*, the onset date will be set to January 1 of the year of onset.

If the *end date of a therapy* is missing both the *day and month*, the date will be set to December 31 of the year of occurrence.

If the *start date of a therapy* is missing and the *end date* is not a complete date then the start date will be set to the date of the first study visit.

If the *start date of a therapy* is missing and the *end date* is a complete date and the end date is after the date of the first study visit then the start date will be set to the date of the first study visit.

otherwise the start date will be set to the end date of the therapy.

If the *end date of a therapy* is missing and the *start date* is not a complete date then the end date will be set to the date of the last study visit.

If the *end date of a therapy* is missing and the *start date* is a complete date and the start date is prior to the date of the last study visit then the end date will be set to the date of the last study visit.

otherwise, the end date will be set to the start date of the therapy.

Confidential Page 40 of 40
